**10.2 Imaging Data**

Date/Time of first imaging	dd/mm/yyyy HH:MM
Most advanced type of imaging performed	
 
● Plain film radiograph
 
● Non-contrast CT Scan
 
● Contrast CT Scan
 
● MRI Scan
 

Anatomical area of spine included on imaging (Can select multiple)	
 
● Cervical
 
● Thoracic
 
● Lumbar
 
● Sacral
 

Level of fracture	
 
● Upper cervical
 
● Subaxial
 
● Thoracolumbar
 
● Sacral
 
● No injury
 

AO Classification of Injury	
Subluxation/Translation	
 
● Yes
 
● No
 

Traumatic herniated nucleus pulposis (not required if only plain radiograph available)	
 
● Yes
 
● No
 
 
If Yes:
 
 
● Please specify level:
 
● Cord compression: Yes/No
 

Haematoma (not required if only plain radiograph available)	
 
● Yes
 
● No
 

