### **1.1 Primary Objective**

- Characterise case-mix, processes of care and variations in nonoperative and operative management strategies, including emergency, ward, surgical and ICU care, in patients presenting with traumatic spinal injury (TSI) between centres across low and high Human Development Index (HDI) countries

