### 3.5 Study measures

The following categories of routine clinical data will be collected prospectively for all patients included in the study. The full data set is included in *Appendix A*.

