#### Imaging data

- Imaging modalities utilised for radiological characterisation of injury
- Injury classification e.g. AO Spine classification

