## **5. Statistical Analysis**

Anonymised data will be analysed by the central study team. Fundamentally the main analysis will consist of a quantitative description of case-mix and the variations in processes of care. Identification and description of areas where known best practice is lacking or unavailable will be performed. This will enable identification of potential targets for future implementation studies.

In addition, early outcomes will be assessed to identify case-mix and process factors that may form a substrate for intervention. Participating centres will be stratified based on their country into groups based on their Human Development Index (HDI). The Human Development Index is calculated for each country based on its life expectancy at birth, years of schooling and gross national income (GNI) per capita.

Specifically, after data validation and curation, the primary analysis will comprise of (1) statistical descriptive analysis of patient-level registry variables, (2) characterisation of processes of care using statistical descriptions of both provider profiling data and patient-level process variables followed by a description of typical process groupings. This will follow and extend methodologies that have previously been applied successfully to traumatic brain injury. Case-mix and process analysis will be stratified in a nested way by site, country, and association with human development index (HDI).

Analysis for the secondary objectives will consist of a quantitative statistical summary of non-operative and operative management. Intra- and inter-site variances will be compared and associations with HDI and process of care factors sought.

Whilst only short-term outcomes can be obtained in this pragmatic point-study, outcomes analysis will be attempted for early mortality, functional status as assessed using the 5-point Frankel Grade, neurology, adverse events and trajectory from admission to 6 weeks post-injury (or discharge or death, whichever occurs first). These will be analysed by HDI group in an appropriate nested model accounting for random effects of site and country. Either ordinal models (for statistical power) or dichotomised models will be used depending on the statistical properties of the data and suitability of model assumptions. Mixed effects models will be used to assess the relationship between HDI and deterioration in functional status at 6 weeks while controlling for confounding variables.

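### The form records only the highest imaging modality, so CT use is unknown in patients who had MRI and plain-film use is unknown in patients who had CT or MRI

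*Combined protocol and SAP*

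**What the plan says.** The Imaging data list in section 3.5 (Study measures) names "Imaging modalities utilised for radiological characterisation of injury", and section 3.5 points to Appendix A as the complete data set. In Appendix A, section 10.2, the only modality item is "Most advanced type of imaging performed". Its four options are plain film, non-contrast CT, contrast CT and MRI. Nothing on the item invites more than one answer. The next item, "Anatomical area of spine included on imaging (Can select multiple"), does so explicitly, so the form marks multiple choice where it is meant.

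The imaging time field, "Date/Time of first imaging", is not linked to a modality.

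On use of the data, the primary objective (section 1.1) is to "Characterise case-mix, processes of care and variations in nonoperative and operative management strategies". Section 5 plans "characterisation of processes of care using statistical descriptions of both provider profiling data and patient-level process variables", stratified by site, country and HDI.

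**The concern.** A patient who had plain film, CT and MRI is stored exactly like a patient who had MRI alone. The recorded CT category therefore means that CT was the highest modality reached, not that the patient had CT. The plain-film category means plain film and nothing more.

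In a descriptive study the recorded process variables are the product, and imaging is a basic step in spinal injury care. The information lost depends on how much MRI a site does, and MRI use plausibly varies with resources, which is the axis of comparison. A table by HDI group that reads the categories as use of each modality could show a CT gap where there is none, hide a real one, or give it the wrong sign. The same figures could enter the search for gaps in best practice (section 1.2) and for candidate performance indicators (section 5). Section 6 (Limitations) does not mention this.

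**Working it through.** **No figure to reproduce.** The documents give no imaging rates, and no sample size or power statement bears on this point. The check asks what the recorded item can identify. All rates below are assumptions.

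**Can another source fill the gap?**
- Time of first imaging and anatomical area (section 10.2) carry no modality.
- The herniation and haematoma items (section 10.2) may be skipped when only a plain radiograph exists. That separates plain film only from the rest, which the modality item already does.
- Provider profiling (section 3.2) describes site caseload, frameworks and resources, not what each patient received.
- The local validator (section 4.2) records admission date, age, AO type and operations, not imaging.

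None recovers CT use in MRI patients, or plain-film use in CT or MRI patients.

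**Identification.** Take the options as ranked in the order listed, with the two CT options combined and no missing data. At a site, let *m* be the share recorded as MRI, *r* as CT and *p* as plain film, with *m* + *r* + *p* = 100%, because inclusion requires radiographic confirmation.
- Known exactly: any MRI = *m*; CT or MRI = *r* + *m*; plain film only = *p*.
- True CT use lies between *r* (no MRI patient had CT) and *r* + *m* (every MRI patient had CT). The width is *m*.
- True plain-film use lies between *p* and 100%.

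**Example.** With *r* = 35% and *m* = 60%, *p* = 100 − 35 − 60 = 5%. True CT use is 35% to 35 + 60 = 95%. True plain-film use is 5% to 100%.

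**Effect on a comparison.** Suppose true CT use is 90% at every site and MRI is given independently of CT. Recorded CT is then 90% × (1 − *m*):

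| MRI use | Recorded CT | CT use compatible with the record |
|---|---|---|
| 0% | 90% | 90–90% |
| 10% | 81% | 81–91% |
| 30% | 63% | 63–93% |
| 50% | 45% | 45–95% |
| 80% | 18% | 18–98% |
| 90% | 9% | 9–99% |

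Compare the 50% and 10% MRI sites. Recorded CT differs by 45 − 81 = −36 points, although true use is equal. From the record alone, the true difference could be anything from 45 − 91 = −46 to 95 − 81 = +14 points, so even its sign is not identified.

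**Is the direction fixed?** No. Under the same independence assumption:
- no CT and no MRI: recorded CT 0%;
- true CT 20%, no MRI: 20%;
- true CT 30%, MRI 5%: 30% × 0.95 = 28.5%;
- true CT 90%, MRI 60%: 90% × 0.40 = 36%.

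Here the site with the most MRI also has the highest recorded CT.

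**The case against.** The best defence is that the item is sound under its own label. As a distribution of highest modality reached it is unbiased, and it identifies plain film only and CT or MRI, both directly relevant to comparing high- and low-resource settings. Section 5 never specifies a CT or plain-film rate, so no planned analysis is shown to misread the item. Section 3.5 lists broad categories, and its plural may refer to the range of modalities across patients. A single ranked item also limits burden in a pragmatic study whose data set was refined with clinicians from low and high HDI countries. Finally, if every MRI patient also had CT, true CT use is exactly recorded CT plus recorded MRI (35 + 60 = 95% in the example).

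Most of this stands, and it limits the point to readings of the item as use of each modality. The last argument does not close the gap: universal CT before or alongside MRI is only the upper bound, the documents do not state it, and the data collected cannot test it.

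Three stronger readings should be resisted:
- A reader might infer that CT use will look lowest wherever MRI use is highest. That does not follow. Any primary, secondary or tertiary institution may join (section 3.1.1), and a site without CT records 0%.
- A reader might infer that nothing about CT can be learned. CT or MRI is known exactly, and CT use is bounded.
- A reader might infer that a select-all item would show which scan the AO class rests on. It would only identify patients with MRI and no CT; for those with both, the question stays open.

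**Conclusion.** The point holds in limited form. With the item in Appendix A, use of CT in MRI patients and of plain film in CT or MRI patients is not identified, and no other field supplies it. The uncertainty in a site's CT rate equals its MRI share: 10 points at 10% MRI, 60 points at 60%. Comparisons of CT or plain-film use by site, country or HDI can be masked or reversed if the categories are read as use of each modality. Reported strictly as highest modality reached, the item is not biased.

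This assumes that Appendix A matches the live form and that the options are ranked as listed. The bounds need no assumption about how CT and MRI overlap; the table of recorded CT does (independence, 90% true CT use). The issue is a cheap improvement to a variable within the primary objective, not a threat to the study as a whole.

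**What to change.** Change the item to *Imaging modalities performed (select all that apply)* and derive the highest modality from it. The reverse derivation is impossible. Report the proportion receiving each modality by site, country and HDI. Missing data aside, the interval for CT use then shrinks from the width of the MRI share to zero.

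The cost is one field changed from single to multiple choice and one or two extra ticks per patient. The skip rule for patients with only a plain radiograph still works.

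If the form can no longer change, label and report the item only as highest modality reached, give the lower and upper bounds for CT use in each stratum, and reword the imaging line in section 3.5 to match. This costs no data collection, but per-modality use stays unknown.

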## Background

Traumatic spinal injury (TSI) is an umbrella term for injuries to the spinal cord, nerve roots, osseous structures, and disco-ligamentous components of the spinal column. Traumatic spinal cord injury (SCI) is a subset of TSI which is most commonly reported in literature. TSI represents a significant global disease burden, recently reported to be 1.6 times higher in low- to middle-income countries (LMICs) than high-income countries (HICs). Furthermore, ongoing indirect costs of severe disability secondary to TSI are a recognised socioeconomic burden, which may disproportionately affect LMICs.

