### 4.2 Data Validation

A number of steps have been taken to ensure validation of all data entered.

- I. The dataset, web-based case report forms, and curation process has been designed according to DAQCOR principles.
- II. Web-based forms in the ORION platform contain fixed options at the point of data entry to maximise the likelihood of accurate and complete data capture at the point of collection.
- III. A local data validator independent to the local study team will be appointed at every participating institution. They will have access to a separate platform on Orion to ensure blinding to the rest of the data collected at their institution. They will be asked to complete a two-phase validation process, with a specific ORION validation user guide available to guide them through the process.
  - a. Prospective Case Acquisition: During the selected 4-week inclusion period, the local data validator will be asked to independently identify and collect all patient cases suitable for inclusion in the study. For validation, they will be required to prospectively collect these cases, recording the admission date, age at admission and AO injury type. This will subsequently be correlated with the data collected by their local team by the central study team.
  - b. Retrospective Operative Data: At 10 weeks from the start of the inclusion period (6-weeks following the end of the inclusion period), the local data validator will be asked to independently access operating theatre logs over the preceding 10 weeks. They will be required to document all the patients who have had an operation for TSI during this period and input the date and type of operation into the validation system where this corresponds to a patient admitted during the inclusion period. This will be used by the central study team to validate this specific cohort of their institution's cases.

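### Disc and haematoma items cannot separate 'absent' from 'not assessable' on CT, AO type has no imaging condition, and no breakdown by modality is planned, so HDI differences in these descriptors may partly reflect scanner access

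*Combined protocol and SAP*

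**What the plan says.** Section 10.2 of Appendix A lists the imaging items.

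- The disc item is "Traumatic herniated nucleus pulposis (not required if only plain radiograph available"), with Yes and No as its answers, followed by level and cord compression if Yes.
- The haematoma item is "Haematoma (not required if only plain radiograph available"), again with Yes and No.
- "AO Classification of Injury" is listed with no condition on imaging. Its answer cell is empty in the text available to us.
- "Most advanced type of imaging performed" is recorded for every patient: plain film, non-contrast CT, contrast CT or MRI. "Anatomical area of spine included on imaging (Can select multiple") is recorded too, but not which modality covered which region.

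Section 4.2 says "Web-based forms in the ORION platform contain fixed options at the point of data entry". Section 3.1.2.1 asks for radiographic confirmation and sets no minimum modality. The Background defines TSI as "injuries to the spinal cord, nerve roots, osseous structures, and disco-ligamentous components of the spinal column", so soft-tissue injury is within scope.

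On analysis, Section 5 states: "Case-mix and process analysis will be stratified in a nested way by site, country, and association with human development index (HDI"). Imaging modality is not named there as a stratum or a covariate. The confounders for the HDI outcome model are not listed, and the between-site comparison will correct for whatever features the descriptive stage brings out.

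**The concern.** The waiver shows that the sponsor accepts two things: some patients will have plain film only, and whether a finding can be recorded depends on the imaging done. The form applies this at one boundary (plain film against everything else) and to two items. Between CT and MRI it makes no distinction, and for AO type it makes none at all.

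A 'No' from a patient with MRI and a 'No' from a patient with CT alone may not carry the same information, yet they are stored as the same value. If MRI is less common in one HDI group, under-recording is concentrated in that group. A larger sample does not remove this. Comparing case-mix across HDI is the primary objective (Section 1.1), so the possible distortion lies along the study's main contrast. The Background expects infrastructure and resources to differ between settings, which makes unequal imaging plausible but does not show it.

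The form can already express uncertainty elsewhere: Section 10.1 offers 'Unknown' for the site of cord injury and for fracture level.

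**Working it through.** **Reading the fields.** The documents state no sample size, imaging share or detection rate for this point, so there is no figure to reproduce. Taking the items as printed:

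| Most advanced imaging | Disc, haematoma | AO type |
|---|---|---|
| Plain film only | Waived; handling of blanks not stated | No condition printed |
| CT, no MRI | To be answered; Yes or No | No condition printed |
| MRI | To be answered; Yes or No | No condition printed |

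**Disc-type finding: model and assumed inputs.** None of these inputs is from the documents. True prevalence π is the same in both HDI groups, there are no false positives, and MRI detects 0.95. CT detects c. The MRI share m is taken among patients with CT or MRI, and is assumed higher in the high-HDI group.

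Recorded prevalence = π × [m × 0.95 + (1 − m) × c]

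Worked line with π = 0.20, c = 0.5, m = 0.70 (high HDI) and 0.20 (low HDI):
- High: 0.20 × (0.665 + 0.150) = 0.163
- Low: 0.20 × (0.190 + 0.400) = 0.118
- Odds ratio: (0.163/0.837) / (0.118/0.882) = 1.46, where the truth is 1.00

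Range at π = 0.20:

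| CT detection c | MRI share 70% vs 20% | MRI share 50% vs 30% |
|---|---|---|
| 0.3 | 15.1% vs 8.6%, OR 1.89 | 12.5% vs 9.9%, OR 1.30 |
| 0.5 | 16.3% vs 11.8%, OR 1.46 | 14.5% vs 12.7%, OR 1.17 |
| 0.7 | 17.5% vs 15.0%, OR 1.20 | 16.5% vs 15.5%, OR 1.08 |
| 0.95 (equal to MRI) | 19.0% vs 19.0%, OR 1.00 | 19.0% vs 19.0%, OR 1.00 |

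Over π from 10% to 30%, c from 0.3 to 0.7 and these two pairs of MRI shares, the odds ratio runs from 1.07 to 1.98. With equal MRI shares (40% in both groups) it is 1.00 whatever c is.

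**If waived plain-film blanks were counted as 'No'.** Assume plain film only in 5% (high) and 40% (low), with the worked line for the rest:
- High: 0.95 × 0.163 = 0.155
- Low: 0.60 × 0.118 = 0.071
- Odds ratio: 2.40

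**The denominator matters.** Take π = 0.15, c = 0.4 and MRI shares of 60% vs 20%.
- If those are shares of CT-or-MRI patients: 0.15 × (0.570 + 0.160) = 10.95% vs 0.15 × (0.190 + 0.320) = 7.65%, a prevalence ratio of 1.43.
- If they are shares of all patients and 5% vs 40% are waived, the MRI share among those answering is 0.60/0.95 = 63% vs 0.20/0.60 = 33%. Recorded prevalence is then 11.2% vs 8.75%, a ratio of 1.28.

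**AO type.** Assume 30% in both groups have a type that depends on soft-tissue disruption, that plain film recognises 60% of these, that other imaging recognises all of them, and that plain film only is used in 5% vs 40%:
- High: 0.30 × (1 − 0.05 × 0.40) = 29.4%
- Low: 0.30 × (1 − 0.40 × 0.40) = 25.2%
- Gap: 4.2 points. It is 2.1 points at 80% recognition and 5.3 at 50%.

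**Comparison within modality.** Holding modality fixed brings the odds ratio back to 1.00 in this model. That is so only because the model assumes equal detection within a modality and no difference between HDI groups in who is selected for MRI.

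**The case against.** The strongest reply is that the plan already holds what is needed. Modality is captured per patient, provider profiling covers site resources, and Section 5 promises a description of patient-level and process variables, of which modality is one. Section 5 also allows for confounders. All this stands as far as it goes: an analyst could do the right thing. But no commitment to a breakdown by modality is made, and a CT 'No' cannot afterwards be split into its two meanings.

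It is also fair that every magnitude above is assumed. The distortion needs both unequal modality mix and missed findings, and the documents establish neither.

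Several stronger readings are tempting and are not supported:

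- *The form defaults to 'No' on CT.* No default is described, and nothing says a blank on CT is rejected. What the text supports is that the item is to be answered and only two answers are printed.
- *AO type lacks an 'unclassifiable' answer.* The AO answer cell shows no answers at all. Section 10.4 refers one of its own items to a flow chart on the platform, so AO options may also sit there. Only the missing imaging condition can be shown.
- *Injury severity as a whole is biased.* Frankel grade, GCS and Kampala Trauma Score do not use these items. Only three imaging-based descriptors are at issue.
- *The outcome models are biased.* Section 5 does not name AO type, disc herniation or haematoma as covariates. The risk exists only if one of them enters.
- *The validator's match on AO type is weakened.* The validator works at the same institution and presumably sees the same imaging, so limited imaging need not cause disagreement.

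**Conclusion.** The point holds in a limited, conditional form. As printed, the disc and haematoma items merge 'absent' with 'not assessable' for patients with CT but no MRI, AO type is asked without regard to modality, and Section 5 does not commit to separating modalities when HDI groups are compared. If modality mix differs by HDI and less advanced imaging misses findings, the HDI contrast in these three descriptors is confounded with scanner access.

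The illustrative size is a spurious odds ratio of 1.07 to 1.98 for a disc-type finding, 2.40 in one scenario that also counts waived blanks as 'No', and a gap of 2.1 to 5.3 points for AO type. All of these rest on equal true prevalence, no false positives and assumed imaging shares and detection rates. They show what is possible and are not estimates for this study.

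A reader might infer that the CT-or-MRI subset, or MRI patients alone, gives the true comparison. Neither does. Pooling CT with MRI keeps the CT–MRI difference, and restricting to MRI conditions on who is sent for MRI, which may itself vary with HDI. The point is worth acting on because the remedy is cheap and the contrast is the primary one, but it does not undermine the study's other severity measures.

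**What to change.** 1. **Form (Section 10.2).** Add 'Not assessable on imaging performed' to the disc and haematoma items, and to AO type if the platform does not already offer it. Tell sites that this answer is a judgement about the imaging, not about whether a lesion was seen. Report it as its own category: if it were dropped from the denominator, CT positives would stay while unclear CT negatives left.
2. **Analysis (Section 5).** Report AO type, disc herniation and haematoma by most advanced modality within HDI group, alongside the overall figures. Name no single subset as the comparison to interpret. State that selection for MRI may differ by HDI, and that the most advanced modality may not have covered the injured region, since the form does not link the two.
3. **Blanks.** Treat items waived for plain film as not assessed, never as 'No'.
4. **Models.** If AO type or another imaging descriptor enters an HDI or between-site outcome model, add a sensitivity analysis that accounts for modality.

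The cost is a few added answer options, some extra tables and smaller denominators within modality. No new patients or procedures are needed. If the form can no longer be changed, items 2 to 4 can still be done with fields already collected, although CT answers already entered would keep their ambiguity.
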